Participants will be males and females at least 15 years of age, recruited from the University of Connecticut Health Center (UCHC) and Gaylord Specialty Healthcare Physical Therapy, (GSHPT). Potential study participants will be identified upon evaluation by members of the UCHC and GSHPT clinical teams based on their presentation of PFPS. A clinical diagnosis indicated by a referring physician or the physical therapist conducting the initial evaluation is needed to participate in the study. Clinical history entails a review of previous medical records documenting knee pain, symptoms, treatments, and outcomes along with any current referral notes from outside clinicians and the participant's completed self-assessments which are done before the PT evaluation. According to the Journal of Orthopedic Sports Physical Therapy, PFPS is diagnosed by (1) the presence of retropatellar or peripatellar pain, (2) reproduction of retropatellar or peripatellar pain with squatting, stair climbing, prolonged sitting, or other functional activities loading the PFJ in a flexed position, and (3) exclusion of all other conditions that may cause anterior knee pain, including tibiofemoral pathologies. The physical exams GSHPT use includes meniscal tests, ligamentous stress tests and joint specific loading tests to rule out more specific injuries. The combination of findings from both the clinical history and physical exam and the diagnoses, allows the PT to exclude leads to the last catchall diagnosis, which is PFPS. There is not a clearly defined test or process to determine a PFPS diagnosis, so clinical judgment is relied upon for the ultimate diagnosis.

The clinical diagnosis is determined by an integration of both clinical history and physical exam findings, as well as by excluding other musculoskeletal and medical problems with thorough assessment of clinical history, risk factors, and physical examination. This is an exclusionary diagnosis that presents with generalized anterior knee pain surrounding the patella after excluding other sources of AKP such as patellar tendinopathy, trauma injury and arthritis.

To be eligible for study participation, subjects must meet the following Inclusion Criteria:

Diagnosis of patellofemoral pain syndrome (PFPS), which may be listed as non-specific anterior knee pain (NSAKP) of one or both knees, and plan to attend a participating GSHPT site.

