Those who present one or more of the following Exclusion Criteria will not be eligible for study participation, including:

- Member of a defined vulnerable population, women who are or suspected to be pregnant, prisoners, children under 15, or other protected populations
- Body mass of the leg preventing the cuff from fitting properly
- Radiographic evidence of osteoarthritis (\geq Kellgren-Lawrence Grade 2)
- History of intra-articular injection into either knee within 3 –months
- Uncontrolled or untreated inflammatory disorder
- Acute inflammatory disorder
- Uncontrolled Diabetes and/or peripheral neuropathy, impaired circulation
- Uncontrolled cardiac conditions including uncontrolled hypertension
- Areas of thrombophlebitis, thrombosis
- Distal wounds or pain below the knee that is $>4/10$. This level is self-reported by the patient and is based on the Numeric Pain Rating Scale. Patients are asked to rate their pain level on a 0 to 10 scale with 0 being no pain at all and 10 being the worst pain imaginable. Typically, a pain level of 4 or greater is considered the clinical cutoff for continuation or inclusion in a treatment or activity.
- History of or current rhabdomyolysis
- Prolonged immobilization (>3 months)
- Sickle cell anemia
- Lymphadenectomy
- Varicose veins, or a history of personal or immediate family history (parental or sibling) of deep vein thrombosis
- Current infection at or below the level of cuff placement
- Malignancies in or below the area to be treated
- Other conditions/medications that would interfere with subject safety or data collection in the opinion of the PI
- Subjects with an increased risk of non-response as determined by the therapist
- Once entered in the study, a diagnosis change that affects participation. These diagnoses may be pregnancy, a new infection below the cuff level or one that could not be determined until the patient began and in some cases completed PT. Patients whose insurance will not cover imaging tests until they have completed a PT series are eligible since they are presenting with PFPS and

may be in search of a diagnosis. They and their PT are progressing through the exploratory and exclusionary process and if warranted by the Exclusion Criteria will be removed from the study.

Equipment and Instruments:

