Several pieces of equipment and outcome instruments will be utilized in this study. SmartCuffs (Smart Tools Plus, LLC, Cleveland, OH) Blood Flow Restriction Cuffs will be the primary piece of equipment used to complete the intervention portion of this study. The SmartCuff has a Personalized Pressure feature built into it. This feature allows for a personalized pressure calculation based on the patient's limb dimensions and blood flow. With the built-in pressure sensor and on-board computer, it will calculate and set the optimal pressure needed without the need for an external doppler probe or hand pump used by the PT. All study locations utilize this automated BFR cuff. Staff will be trained and/or retrained to ensure consistent practice across sites.

To obtain objective strength measures across the patient's treatment duration, isometric handheld dynamometry using a Mark-10 force gauge, model M3-500 (max capacity of 500 lb force/250 kg force/2500 newton force), will be completed by named investigators at initial evaluation, at 4-weeks, and at either the 9-week or discharge evaluation, whichever is first.

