Potential study participants will be identified via initial physical therapy evaluation as demonstrated clinical diagnosis. Clinical diagnosis is determined by an integration of both clinical history and physical exam findings, as well as by excluding other musculoskeletal and medical problems with thorough assessment of clinical history, risk factors, and physical examination. People may come to GSHPT with a diagnosis already in place, or they may be diagnosed by the Physical Therapist conducting the exam. Recruitment for the study will take place at four GSHPT locations: Cheshire, Cromwell, Madison, and Wallingford. Referrals for possible eligible participants for knee pain related physical therapy may be made by the usual outside referral sources. The study recruitment flyer will be shared with some of GSHPT's usual referral sources.

Once a diagnosis is reached, the patient will meet with a member of the study team. If the patient meets all inclusion and exclusion criteria, a study team member will begin the process to obtain informed consent. Consent will occur before any enrollment and treatment procedures are performed.

Subject assignment:

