Consented subjects will be assigned to either the sham-comparator control group or BFR Intervention Group according to a pre-generated randomized assignment sheet. Each randomized assignment sheet will consist of equal control and equal BFR assignments whose order has been randomized using the random list generator at <https://www.random.org/lists/>. We will use blocked randomization to reduce the risk that patients will be assigned to the BFR treatment and sham control groups at unequal frequencies. These blocks will have a size of 6. Co-Investigators at each site will be given a unique list with a number of assignments that is in proportion to the number of subjects expected to be recruited at the site; additional assignment lists will be generated if needed. These co-Investigators will be responsible for communicating group assignments to study therapists delivering the intervention, and for ensuring that randomization and treatment order is maintained. It is expected that if the assignment scheme is not maintained for whatever reason, that they will report the incident to the PI and how it was/or still needs to be rectified. No matter group assignment, all consented subjects will be asked to conduct all assessments. Utilizing a proposed sample size of 96 participants, the study will continue until there are at least 40 participants who complete all study related activities in both the intervention and control groups.

Study protocol:

After being identified as a potential study participant and being consented, participants will be randomly assigned to the sham control or BFR group. All physical therapy sessions will consist of typical, standard

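### Each site's full assignment list is held by a co-investigator at that site, and nothing in the plan hides the next assignment from staff who judge eligibility or take consent

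*Combined protocol and SAP*

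**What the plan says.** Under Subject assignment (section 1.1), allocation is 1:1 from sheets generated in advance with an online list randomiser. On block size the plan states: "These blocks will have a size of 6". On custody: "Co-Investigators at each site will be given a unique list with a number of assignments". On release: "These co-Investigators will be responsible for communicating group assignments to study therapists delivering the intervention". The co-investigators must also keep the order and report any departure from the scheme to the PI.

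Under Subject identification, recruitment, and pre-assessments: "Potential study participants will be identified via initial physical therapy evaluation". When the criteria are met, "a study team member will begin the process to obtain informed consent". Which team member does this is not stated. Consent precedes random assignment.

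Two parts of the entry decision rest on judgement. Participants and Settings gives three diagnostic criteria but adds that no defined test exists, "so clinical judgment is relied upon for the ultimate diagnosis". One exclusion criterion reads "Subjects with an increased risk of non-response as determined by the therapist", with no definition of that risk. Another leaves exclusion to the opinion of the PI.

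The opening of section 1.1 says that investigators cannot be masked to the intervention.

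**The concern.** Concealment means that nobody deciding whether and when a patient enters can know or predict the arm that comes next. It is separate from masking during treatment, and it is achievable even where masking is not. Here the whole future sequence for a site sits with an investigator at that site, and the plan places no barrier between that person and the entry decision.

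Staff who know the next arm can, without intending to, hurry one patient in, put another off, or conclude that a third is unlikely to respond. The arms then differ in prognosis at entry. Adjusting for measured baseline variables removes only part of this, because the judgement may rest on things that were never recorded. Allocation is also one of the few protections this trial has: delivery and assessment are unmasked and most outcomes are self-reported.

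**Working it through.** **Text check.** The steps from evaluation to treatment, with what the plan says about knowledge of the next assignment:

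| Step | Who | Barrier to knowing the next arm |
|---|---|---|
| Diagnosis, identification | clinical teams, evaluating therapist | none stated |
| Criteria met, consent | an unspecified study team member | none stated |
| Custody of the list | co-investigator at the site | not barred from the steps above |
| Release to treating therapist | the same co-investigator | comes after consent |
| Departure from the scheme | reported to the PI | after the fact |

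Consent before assignment fixes the order of events only. Reporting to the PI can catch an assignment given out of order. It cannot catch a patient who was delayed or never approached.

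**The plan's own figure.** For a two-sided t-test with alpha 0.05, power 0.80 and effect size 0.635 (Sample size), the calculation gives 39.9 per arm, so 40 per arm and N = 80. The plan's figure is reproduced, and 40 per arm is used below.

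**Predictability.** A block of 6 with 3 per arm has 20 possible orders.
- Someone who reads the list knows 100% of upcoming assignments.
- Without the list, but with all earlier site assignments and the block boundaries known, an assignment is certain once one arm is used up. Averaged over the 20 orders, this is 1.5 of 6 = 25%, or 24 of 96 if all blocks are completed.
- Guessing the arm that is behind so far (a coin toss when level) is right for 4.1 of 6 = 68.3%.

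The last two are upper bounds for a single therapist, who would not normally see every assignment at the site.

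**What steering could do (illustration).** The documents give no size for such a shift, so a range is assumed. Let η be the shift in prognosis, in SD, applied in both directions: patients η better than average are entered when one arm is expected, and η worse when the other is. Let f be the share of enrolments steered and p the probability that the expected arm is right. With no true effect:

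spurious difference = 2 × η × f × (2p − 1)

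Example: η = 0.1, f = 1, p = 1 gives 2 × 0.1 × 1 × 1 = 0.20 SD. Guessing gives 2 × 0.1 × 1 × (2 × 0.683 − 1) = 0.073 SD.

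Type I error is that of a two-sided 5% normal test whose statistic is shifted by the spurious difference × √(40/2).

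| Scenario | p | f | Spurious difference (SD) at η = 0.05 / 0.1 / 0.2 | Type I error |
|---|---|---|---|---|
| List seen, all steered | 1 | 1 | 0.10 / 0.20 / 0.40 | 7.3% / 14.5% / 43% |
| List seen, half steered | 1 | 0.5 | 0.05 / 0.10 / 0.20 | 5.6% / 7.3% / 14.5% |
| List seen, a quarter steered | 1 | 0.25 | 0.025 / 0.05 / 0.10 | 5.1% / 5.6% / 7.3% |
| Guessing only, all steered | 0.683 | 1 | 0.037 / 0.073 / 0.147 | 5.3% / 6.2% / 10.1% |
| Concealed | 0.5 | any | 0 | 5.0% |

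In the first row the spurious differences are 0.10/0.635 = 16%, 0.20/0.635 = 31% and 0.40/0.635 = 63% of the planned effect. A noncentral t with 78 degrees of freedom gives 7.3%, 14.3% and 42.4% for that row, so the normal approximation does not drive the result.

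**The case against.** The plan does separate some roles. Treating therapists are told assignments and are not given the list; clinical teams identify candidates; the study team meets the patient only once a diagnosis has been made. The diagnosis and the non-response exclusion therefore belong to clinicians, while the list belongs to co-investigators. This stands, and it narrows the open overlap mainly to final eligibility and consent. It does not close the gap, because nothing prevents a co-investigator from being the evaluating therapist or the person who takes consent.

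The strength measurement that "will be completed by named investigators at initial evaluation" is weak evidence of overlap. The protocol describes it as routine on admission for knee pain and does not say that those investigators hold lists or judge eligibility. The concern does not depend on it. Strength is also a measured outcome, so not every endpoint is self-reported.

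The type I error figures rest on assumed shifts, and the 43% needs full list access, every enrolment steered and a 0.2 SD shift in both directions. That is correct. The firm figures are those for predictability; the table shows only how the harm scales, and its mild cases lie close to 5%.

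Finally, the sites may conceal the list in practice without saying so. The documents cannot settle that, but the custody rule as written does not require it.

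**Conclusion.** The concern holds. The plan places each site's complete list with an investigator at that site, and contains no step that conceals the next assignment or keeps the list holder away from eligibility and consent. That conclusion rests on the text alone.

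Foreknowledge is complete for anyone who sees the list and at most 68% for someone guessing from past assignments, so custody of the list is the main issue and block size a minor one. The size of any resulting bias is unknown. Under the assumed shifts it runs from negligible (5.1%) to severe (43%). The point should be fixed, because analysis cannot fully remove the bias afterwards. It does not by itself make the trial invalid.

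**What to change.** Amend the Subject assignment paragraph of section 1.1 to state three things:

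1. **Custody.** The site-specific lists are held by a named study role that does not screen, consent or treat at that site. Alternatively, each site receives sequentially numbered, opaque, sealed envelopes prepared by someone outside enrolment.
2. **Release.** One assignment is released at a time, only after eligibility, consent and baseline measures have been recorded for that patient.
3. **Separation.** Whoever holds the list takes no part in eligibility or consent at that site.

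Blocking and separate site lists can stay. Mixing block sizes (for example 4, 6 and 8, order undisclosed) is an optional extra. In a simulation with unknown boundaries it cut assignments known with certainty from 25% to about 2%, but left the best guess at about 67%, so it does not replace moving the list.

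The cost is a one-paragraph amendment with its ethics review, and a call or an envelope per enrolment. Sample size, treatment and visits do not change. The documents do not describe staffing, so the sponsor must confirm that an off-site custodian is available; if not, envelopes serve. If enrolment has begun, the change protects only later participants. If the roles are already separated in practice, stating the custody and release procedure is enough.

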1.2 Data collection and analysis

Along with their standard therapy session reassessments (including routine session notes and progress notes), participants will be asked to complete the PROs at 4-week, 9-week or at the end of PT sessions, 6-month and 12-month intervals. The PROs will be completed by paper and pen while at a therapy session. Baseline, 4-week, and 9-week or end of PT sessions assessments will be completed as part of the routine PT session evaluation process. If the participant is not coming in to Gaylord for appointments, the 6 and 12-month assessments will be completed by phone with the participant or paper copies will be mailed to their last known address. If necessary, an email will be sent to remind them of the study and scheduled assessments.

Information regarding the security of participant's data will be shared with them in the consent form as well as upon request. All information collected specifically for the study will be stored on password protected computers in locked offices. The paper copies of the assessment forms completed as part of routine PT sessions will be stored according to Gaylord procedures in the hard copy of the patient's medical record. Information from the forms will be pulled by study staff and shared across sites only after it is de-identified.

After data is collected and de-identified, it will be analyzed using GraphPad Prism version 9.3.1, or other appropriate statistical software as necessary. Adjustments for abnormal distribution and unequal variance will be applied as necessary. To compare pre- and post-intervention measurements over time on subjective and objective outcome measures, we will use a two-way repeated measures analysis of variance or independent samples t-test to determine the effect of treatment groups (BFR + standard of care therapy and sham + standard therapy). For relationships between variables, we will use correlation and regression analyses as necessary. For categorical data, we will use chi-square testing or Fischer's exact test as necessary. Exact analysis for each test will depend on variance and distribution/normality of data set. We will perform an interim analysis at 50 % participant recruitment in order to assess the effects of the BFR therapy and safety for the subjects, and potential for change in sample size. We will not preclude the possibility of conducting other post-hoc data analyses as appropriate and approved by the IRB.

References

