Several subjective outcome measures will be utilized throughout the study. Function specific subjective outcome measures include: Lower Extremity Functional Scale (LEFS), Knee Injury and Osteoarthritis Outcome Score for patellofemoral pain and osteoarthritis (KOOS-PF), the Tenger Activity Scale, and the Single Assessment Numerical Evaluation (SANE). Pain levels will also be assessed utilizing the Numerical Rating Scale (NRS) Pain Scale, 1-10. The LEFS is a validated 20-question PROM survey used for the measurement of lower extremity function based on the patients' initial function, ongoing progress, and long-term outcome. The KOOS-PF is an 11-question survey that is used to assess five outcomes; they include knee related quality of life, activities of daily living, sport and recreation function, activities, and pain and symptoms. The SANE is a single-item question used globally to assess function. The Numeric Rating Scale is one question pain intensity scale that assesses pain level on a 1-10 scale. The Fear Avoidance Beliefs Questionnaire (FABQ) is a 16 question likert scale questionnaire aimed at assessing how everyday activities assess the patient's current level of pain. The Tenger Activity Scale determines the level of activity prior and post injury. It will be collected at evaluation, 6 months and 12 months. The dynamometry, LEFS, SANE, NRS and KOOS-PF are documented during the initial evaluation, 4-week, and 9-week or at the end of PT. The PROs will be completed at evaluation, 4-week, 9-week or at the end of PT, as well as with a 6 month and 12 month follow-up. See attachment for chart.

Activity	Enrollment	Baseline	4-week	9-week or end of PT	6 months	12 months
Assessed for eligibility			X			
Demographics/baseline activity level			X			
Randomization			X			
Group allocation			X			
PT session			X			
Intervention Group only BFR w/PT	X		X	X		X
Control Group sham BFR w/PT	X		X	X		X
PROs	X	X	X	X	X	X

Subject identification, recruitment, and pre-assessments:

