of care treatment. The treatment plan for people with PFPS who consent to participate will follow a defined schedule of exercises done in conjunction with BFR. This schedule is listed below as Exercise Protocol. The BFR training will be incorporated into the standard therapy sessions and will not elongate the treatment session, quantity of sessions or incur any additional cost. The sham control group will also follow the study Exercise Protocol in their physical therapy sessions. The sham control group will follow a typical standard of care physical therapy protocol based on their ability to complete sets with increased load and repetitions and pain tolerance and have a non-inflated BFR cuff placed in the same position as the intervention group. Similar to the intervention group, as participant's progress in therapy, the Physical Therapist will use their clinical decision making to advance the person through resistance and repetition increases.

A traditional physical therapy evaluation including isometric dynamometry and PROs including the Lower Extremity Functional Scale (LEFS), Knee Injury and Osteoarthritis Outcome Score for Patellofemoral Pain (KOOS-PF), Numeric Rating Scale (NRS), Fear Avoidance Beliefs Questionnaire (FABQ), and the Single Assessment Numerical Evaluation (SANE) will be used for data collection. Dynamometry will be tested at 90 degrees of knee flexion in a seated position with the dynamometer perpendicular to the distal tibia.

The dynamometry measurement is information is routinely collected upon admission to the GSHPT program for people presenting with knee pain. Once in position with an ankle cuff on, the participant will be instructed to perform one warm up test with about 50% effort. They will be cued to "kick slowly into the resistance, ramping up to a moderate effort". After a short rest, they will then be instructed to give 100% effort. Investigators will tell participants to "Kick again into the resistance, ramping up slowly over a few seconds until you are pushing as hard as you can, sustaining this for a few seconds". Participants will be encouraged to give full effort on this second attempt.

Participants will follow the exercise protocol as listed below:

Exercise Protocol

1. A 5-10 minute warm up on a bike or completion of the 6-Minute Walk Test will be utilized to start each session.
2. Establish a 10 repetition maximum (RM) for all exercises, pain dependent

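### The plan does not say whether on-treatment PROs and strength tests come before or after that day's exercise, which is done with an inflated cuff in one arm only, and strength rests on a single maximal kick

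*Combined protocol and SAP*

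**What the plan says.** **Where the measurements are made.** On PROs, section 1.2 (Data collection and analysis) states: "The PROs will be completed by paper and pen while at a therapy session". It then adds: "Baseline, 4-week, and 9-week or end of PT sessions assessments will be completed as part of the routine PT session evaluation process". Section 1.1, Equipment and Instruments, says that dynamometry "will be completed by named investigators at initial evaluation, at 4-weeks, and at either the 9-week or discharge evaluation, whichever is first", and puts strength and the PROs at the same visits: "The dynamometry, LEFS, SANE, NRS and KOOS-PF are documented during the initial evaluation, 4-week, and 9-week or at the end of PT".

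**Order at baseline.** Section 1.1, Participants and Settings, mentions "the participant's completed self-assessments which are done before the PT evaluation". Consent precedes any treatment procedure (Subject identification, recruitment, and pre-assessments).

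**What a session contains.** The Exercise Protocol in section 1.1 starts each session with a warm-up. Each of its two phases lists five exercises, with four sets to failure per exercise. Knee extension is in both phases. One arm exercises at 40-80% occlusion and the other with an uninflated cuff. The warm-up is the only step whose place in the session is given.

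**How strength is tested.** Under Study protocol in section 1.1, "the participant will be instructed to perform one warm up test with about 50% effort". One maximal kick follows: "Participants will be encouraged to give full effort on this second attempt". No repeat or averaging is described.

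**The concern.** Strength and pain at 4 weeks and at 9 weeks or end of PT are meant to show what the weeks of training achieved. Measured after the day's exercise, they would also carry the immediate response to that exercise: loss of force, soreness or altered pain. The test is a seated knee extension, and the session works that movement to failure. The protocol also accepts pain of up to 3 or 4/10 with exercise.

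Both arms exercise, so a response common to both would largely cancel. The part that would not cancel is any immediate response to occlusion itself, because only one arm has it. Randomisation does not remove this, since it follows from the assigned cuff. The assessor is not masked (section 1.1). The plan does not ask for the time of testing, so a shift of this kind could not be identified or adjusted for later.

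The single kick is a different matter. One poor or pain-inhibited effort becomes the recorded value. That is random error in both arms and not bias by arm.

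**Working it through.** **1. The plan's own figure.** Inputs from section 1.1, Sample size: two-tailed t-test, alpha 0.05, power 0.80, effect size 0.635, about 80 complete datasets. The normal approximation gives 39 per arm (78). The exact noncentral-t calculation gives 39.9, so 40 per arm, 80 in total, with power 0.801. The figure reproduces and does not depend on this point.

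**2. Exercise that could precede a test.** 5 exercises x 4 sets = 20 sets to failure, in either phase.

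**3. What the text settles about order.**

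| Measurement | Setting stated | Before or after exercise? |
|---|---|---|
| Baseline PROs | Self-assessments precede the PT evaluation (taking these to be the PROs is a reasonable inference) | Before |
| Baseline strength | Initial evaluation | Before: no study treatment has yet been given |
| 4-week PROs and strength | Routine PT session evaluation | Not stated |
| 9-week or end-of-PT PROs and strength | Routine PT session evaluation; for strength, the 9-week or discharge evaluation | Not stated; Phase 2 is labelled weeks 5-8, so there may be little or no exercise that day |
| 6- and 12-month PROs | Phone or mail if the participant is not attending | Not affected when done by phone or mail |

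No minimum gap since the last session is set either.

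**4. What a shift would do, if there is one.** The documents give no acute effect, so the shift b (between-arm difference, in SD units) is assumed, and zero is included. At 40 per arm the noncentrality is (true effect + b) x sqrt(40/2), with 78 degrees of freedom. For example, with no true effect and b = 0.2 it is 0.2 x 4.472 = 0.894. If b = 0.2 works against BFR and the true effect is 0.635, it is 0.435 x 4.472 = 1.945.

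| Assumed b | False-difference rate, true effect 0 | Power for 0.635, shift against BFR |
|---|---|---|
| 0 | 5% | 80% |
| 0.1 | 7.3% | 66% |
| 0.2 | 14.3% | 48% |
| 0.3 | 26.3% | 32% |

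This shows sensitivity and does not estimate b. The plan does not tie 0.635 to strength or to any other named outcome. It gives no recall period for the NRS, so the sensitivity of that score to same-day soreness is unknown.

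**5. One kick against the mean of three.** With single-trial reliability r and independent trial errors, the variance of the mean of three relative to one effort is r + (1 - r)/3.
- r = 0.80: 0.80 + 0.20/3 = 0.867, a 13% reduction.
- r = 0.95: 0.95 + 0.05/3 = 0.967, a 3% reduction.

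The reliability is assumed; the documents give none.

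**The case against.** The strongest reply is that silence on order does not mean testing after exercise. A reader might infer that baseline and follow-up are taken in different states. The documents do not show that. Section 1.2 puts all three assessments in one sentence and one routine process, and self-assessments precede the evaluation at baseline. A clinic that follows the same routine throughout would test first at follow-up too. This stands: the defect is that the order is unstated, not that a mismatch has been shown. The reply is itself an inference, however, and nothing in the plan binds the four sites to it.

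Three further points carry weight:
- **Exposure is uneven.** It is mainly at 4 weeks, for the reason given in the table on order.
- **Twenty sets to failure sounds harder than it may be.** The Exercise Protocol lets the participant decide when failure is reached, within an acceptable pain level. Both arms do the work, and Romanian deadlifts and hip abduction are not the tested movement. Knee extension is, and it is in both phases.
- **Three kicks instead of one is partly a matter of preference.** The gain is modest and concerns precision only.

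A reader might also infer that therapists who know the arm choose when to test. The documents do not support this: dynamometry is assigned to named investigators, and nobody is given discretion over timing within a session. The lack of masking is disclosed and is a separate matter.

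**Conclusion.** The point holds as a gap in the plan. As written, strength and NRS pain may be measured after exercise that differs between arms by cuff inflation, chiefly at 4 weeks, and at 9 weeks or end of PT if exercise is given that day. Neither the size nor the direction of any resulting shift can be derived from the documents, and it may be zero. The 0 to 0.3 SD range above is an assumption.

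A reader might put a size on it by assuming a 5 to 10 point between-arm difference in acute force loss and a 25% between-subject SD. With all tests after exercise that gives 5/25 = 0.20 to 10/25 = 0.40; with half of them, 0.10 to 0.20. Against 0.635 this is 16% to 63% of the planned effect. It should not be used as evidence of size: neither input is in the documents, and the range leaves out zero.

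The single maximal kick is a secondary point. Under the assumed reliability of 0.95 to 0.80 it leaves a 3% to 13% variance reduction unused. The planned 80 complete datasets are unaffected. The change is worth making because it costs almost nothing, and a shift by arm could not be corrected afterwards.

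**What to change.** **Order.** In section 1.1 (Study protocol) and section 1.2, state that at each on-treatment assessment, in both arms, PROs are completed first and dynamometry second, before the cuff is applied and before any session exercise. Use the same warm-up before the strength test as at baseline, and say what it is.

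**Record.** Add the time of testing and the date of the last therapy session to the data collection form. A fixed gap or a set session of the week is not proposed, because the plan gives no session frequency.

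**Strength.** Replace the single maximal kick with the mean of three maximal efforts, using the stated cue, at every dynamometry visit including baseline.

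**Cost.** Protocol and form wording, and about two more minutes per strength test. There may be slight extra soreness from testing. No added visit, staff or equipment is needed, and sample size and treatment are unchanged. Where a site already tests first, the ordering sentence only writes down current practice.
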